### **8.13.2. Dose Continuation, Dose Escalation and Study Stopping Criteria**

Continuation of dosing within a cohort, or dose escalation to sequential cohorts will stop when either:

- a) The highest dose is reached or,
- b) Clinical/laboratory/AE findings meet any of the following stopping criteria:
  - i. Two or more subjects on active medication have clinical laboratory values meeting the criteria of moderate (Grade 2) intensity
  - ii. Two or more subjects on active medication experience moderate AEs of the same type (within the same MedDRA SOC)
  - iii. One or more subjects on active medication experiences any clinical laboratory value meeting the criteria of severe (Grade 3 or 4) intensity or an AE is determined to be severe in intensity
  - iiii. Any subject has a positive FOBT
- c) The mean kindolor systemic exposure levels exceed  $AUC(T_{last})=87,550$  ng.h/mL or  $C_{max} > 13,490$  ng/mL in a single subject in a cohort.
- d) The DSMB recommends stopping escalation after review of all the data from each cohort.

The maximum tolerated dose (MTD) will be considered the highest dose where no active medication subjects meet the study stopping criteria.

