### 4.8. Rationale for Selection of Doses for this Study

For this first-in-humans study, the FDA “Guidance for Industry: Estimating the Maximum Safe Starting Dose in Initial Clinical Trials for Therapeutics in Adult Healthy Volunteers” was followed by considering the human equivalent dose (HED) in two relevant species (rats and minipigs) evaluated in the nonclinical toxicology studies as shown in Table 4. The basis for the starting dose is the HED in rats, as rats had the lowest HED at the NOAEL. Taking a conservative approach, instead of starting at  $1/10^{th}$  the HED in the most sensitive species (rats), a starting dose in humans of 100 mg was selected which is 82-fold less than the rat HED. The highest dose to be tested in humans is 1800 mg. This dose is below the rat NOAEL at the same HED by 4.5-fold.

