## 5. STUDY DESIGN

This is a Phase 1a, randomized, double-blind, single ascending dose study designed to assess the safety, tolerability, and PK of kindolor tosylate. Healthy male and female adults will be screened for eligibility by medical history, physical examination including height and body weight, vital signs, 12-lead electrocardiogram (ECG), clinical laboratory tests (chemistry, hematology, amylase, lipase and coagulation tests, medical urinalysis, and infectious disease screen), urine drug screen for drugs of abuse, fecal occult blood tests (FOBT), and medication use. Females will have a pregnancy test.

Using a dose escalating design, eligible subjects will receive randomly assigned oral tablets of kindolor tosylate (100 mg and 300 mg strengths) or identically matched Placebo tablets in 4 cohorts of 8 subjects (6 kindolor tosylate and 2 placebo in each cohort). A sentinel cohort of 2 subjects (1 active and 1 placebo) will be dosed and closely monitored for at least 24 hours prior to dosing the remaining 6 subjects in each successive cohort. Ascending doses of kindolor tosylate include 100 mg (1 x 100 mg tablet), 300 mg (1 x 300 mg tablet), 900 mg (3 x 300 mg tablet), and 1800 mg (6 x 300 mg tablet). The safety data for each completed cohort will be reviewed by the UCSD Clinical and Translational Research Data and Safety Monitoring Board (DSMB) that will recommend continuation to the next cohort or stopping the study due to safety concerns.

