## **6. STUDY OBJECTIVES**

### **6.1. Primary Objective**

The primary objective of the study is to determine the safety and MTD of kindolor tosylate in healthy volunteers.

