2 INTRODUCTION

This statistical analysis plan (SAP) for Protocol No. KIND-2022-01, “A Phase 1a Randomized, Double-blind, Placebo-controlled, Single Site, Single Ascending Dose Study of the Safety, Tolerability, and Pharmacokinetics of Kindolor Tosylate in Healthy Adults” describes and expands upon the analytical plan presented in the protocol.

This document contains all planned analyses, reasons and justifications for these analyses for all study data. This plan also includes sample tables, figures, and listings that will be populated. The SAP will follow the International Conference on Harmonization of Technical Requirements for Registration of Pharmaceuticals for Human Use (ICH) Guidelines as indicated in Topic E3 (Structure and Content of Clinical Study Reports), Topic E8 (General Considerations for Clinical Trials) and Topic E9 (Statistical Principles for Clinical Trials). The structure and content of the SAP provides sufficient detail to meet the requirements identified by the FDA and ICH.

The following sources were used in preparation of this SAP:

- Protocol # KIND-2022-01, Protocol Version No.: 8.0; Version Date: 30 August 2024
- ICH Guidance Topics E9, E3 and E8

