3 PROTOCOL SUMMARY

3.1 Study Objectives

Primary: The primary objective of the study is to determine the safety and maximum tolerated dose (MTD) of kindolor tosylate in healthy volunteers.

Secondary: The secondary objective of the study is to determine the PK of kindolor tosylate by quantitating kindolor levels in plasma across a range of doses in healthy volunteers.

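### If no cohort meets a stopping criterion, the protocol's rule labels 1800 mg the MTD, and neither document allows for 'MTD not reached'

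*Protocol*

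**What the plan says.** Protocol 6.1 sets the aim: "The primary objective of the study is to determine the safety and MTD of kindolor tosylate in healthy volunteers". SAP 3.1 repeats it almost word for word.

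Protocol 8.13.2 gives four ways in which escalation ends. Item a reads "The highest dose is reached or". Item b lists clinical, laboratory and AE findings: criteria i and ii need two or more active subjects, iii needs one, and the fourth is a positive FOBT in any subject. Item c is an exposure limit (mean AUC, or Cmax in a single subject). Item d is a DSMB recommendation. The section closes with the only MTD definition in either document: "The maximum tolerated dose (MTD) will be considered the highest dose where no active medication subjects meet the study stopping criteria".

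The ceiling is fixed in advance in Protocol 4.8: "The highest dose to be tested in humans is 1800 mg". Protocol section 5 plans six active and two placebo subjects in each of four cohorts.

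SAP section 2 says of itself: "This document contains all planned analyses, reasons and justifications for these analyses for all study data". After SAP 3.1 the MTD does not appear again. It is absent from the endpoints (3.3), from section 9, and from the lists of tables, listings and figures.

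**The concern.** Reaching the top planned dose is a reason to stop, but it is not something a subject can meet. It therefore does not disqualify 1800 mg under the MTD sentence. A study with no finding at any dose would report 1800 mg as its MTD, although that dose is where the sponsor planned to stop and not where tolerance was seen to end.

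Part of the primary objective is at stake. Readers of the report, and designers of later trials, could take a planned ceiling for a measured limit. The SAP offers no safeguard, because it does not say how the MTD is derived, what is reported if none is found, or where the conclusion appears.

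**Working it through.** **The plan's own figure.** Protocol 12.4 and SAP section 7 give the chance of at least one AE in six active subjects. The formula is 1 − (1 − p)^6. At p = 10%, 15%, 20% and 25% it gives 46.9%, 62.3%, 73.8% and 82.2%. The stated 47%, 62%, 74% and 82% reproduce.

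**What the MTD sentence returns.** I traced it through the ways in which 8.13.2 lets escalation end.

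| Escalation ends because | MTD sentence returns | What the data would support |
|---|---|---|
| Top dose given, all four cohorts clean (a) | 1800 mg | No criterion met up to 1800 mg; no limit located |
| Severe finding on active drug above 100 mg (b iii) | The highest clean dose below it | A clean dose with a finding above it |
| Severe finding on active drug at 100 mg (b iii) | No dose | Not addressed |
| Positive FOBT in a placebo subject only (b) | The dose of that cohort | A stop without a finding on active drug |
| Exposure limit only (c) | Unclear: the mean AUC belongs to a cohort, not a subject | No tolerance finding needed |
| DSMB recommendation only (d) | The current dose | Depends on the DSMB's reason |

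The first row is the main gap. The placebo, exposure and DSMB rows show why the reason for ending escalation should accompany any MTD statement.

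**Subjects or counts.** The sentence speaks of subjects meeting criteria, but i and ii are met by a cohort with two or more affected active subjects. The status of a dose with exactly one Grade 2 laboratory value is therefore open.

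**Is the clean outcome plausible?** The documents give no rates for stopping events, so the rates below are assumptions. The chance that six active subjects do not trigger a one-subject rule is (1 − p)^6. For a two-subject rule it is (1 − p)^6 + 6p(1 − p)^5.

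| Assumed rate at 1800 mg | One-subject rule not met | Two-subject rule not met |
|---|---|---|
| 10% | 53% | 89% |
| 20% | 26% | 66% |
| 30% | 12% | 42% |

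If the same rate held in all four cohorts, the one-subject rule would stay unmet throughout with probability (1 − p)^24: 79% at 1%, 62% at 2%, 29% at 5% and 8% at 10%. Protocol 4.8 also puts the top dose 4.5-fold below the rat NOAEL on the human-equivalent scale (8160/1800 = 4.53), and 4.9 expects low GI risk. A clean study is an outcome the plan should provide for.

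**Precision.** For 0 of 6 the exact upper 95% limit is 1 − 0.025^(1/6) = 45.9% two-sided, or 1 − 0.05^(1/6) = 39.3% one-sided. This describes the cohort size and is not the size of this gap, as discussed in the objection.

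**The case against.** The strongest reply is that the protocol may define its MTD operationally and has done so in advance. Naming 1800 mg would follow that definition. This stands as far as it goes. A reader might infer that half of the primary objective would be answered wrongly. The documents do not support that: the label would comply with the stated rule, and the safety part is untouched. What remains is that a lower bound would be reported under a name that suggests a located maximum.

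A reader might also infer that nothing in the report would reveal an absence of events. That is too broad:
- SAP 9.6 reports whether a GI AE triggered a stopping criterion.
- Tables 7 to 13 give AE severity by dose and for placebo.
- Tables 16 and 20 show positive FOBT by group.
- Table 4 gives mean AUC and the range of Cmax by dose.
- Abnormal laboratory values largely enter the AE tables as graded AEs (Protocol 11.1.4 and 11.3).

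Missing are one output that brings the 8.13.2 criteria together by dose, and any output that states the MTD.

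The 46% limit is tempting as a measure of the problem. It applies to any cohort with 0 of 6, including a clean dose below a toxic one, and the fix leaves it unchanged. The 53% and 26% are complements of the plan's own 47% and 74%, so the small-sample limit is already disclosed.

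Finally, the gap matters only if no cohort is stopped. Reading 1800 mg as an upper limit would, if anything, restrict later dosing. No subject's dose and no escalation decision depends on it. These points lower the severity but do not remove the gap.

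**Conclusion.** The concern holds as a reporting gap in part of the primary objective. With four clean cohorts, the rule in Protocol 8.13.2 names 1800 mg the MTD. The data would support only that no stopping criterion was met up to 1800 mg in six active subjects per dose. Neither document has a not-reached outcome, and the SAP carries the objective without a derivation or output.

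The finding follows from the wording and does not depend on any assumed rate. The assumed rates show only that the outcome is plausible: at 1800 mg, a 10% to 30% rate of a qualifying event leaves a one-subject rule unmet with probability 53% down to 12%. They assume independent subjects and a full cohort of six. Sample size, doses, stopping criteria and collected data are unaffected. Severity is should-fix.

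**What to change.** 1. Add to Protocol 8.13.2 and to SAP section 9: 'If no dose meets the stopping criteria, the MTD was not reached and 1800 mg is reported as the highest dose tested.' Say also what is reported if the first cohort meets a criterion.
2. Report the reason escalation ended (a, b, c or d) beside any MTD statement.
3. Reconcile the MTD sentence, which speaks of subjects, with criteria i and ii, which are counts of two or more. State how a stop on c or d, or on a placebo FOBT, bears on the MTD. The sponsor must settle the reading; the criteria themselves stay as written.
4. Add one SAP table by dose, with pooled placebo alongside. Show whether each 8.13.2 criterion was met (yes/no) and the number of active subjects with each component event: Grade 2 laboratory value, moderate AE by SOC, Grade 3 or 4 laboratory value or severe AE, positive FOBT, Cmax above the limit. Give exact (Clopper-Pearson) 95% intervals for these per-subject counts only. Criteria i and ii are cohort counts, so their yes/no entries take no interval; mean AUC and the DSMB recommendation are shown as values.

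The cost is a few sentences, one table shell and, after a clean study, a less favourable conclusion. SAP 3.2 is partly in the past tense, so dosing may have begun. The rule can still go into the SAP, which Protocol 12.1 requires to be complete before lock and unblinding. Changes to a final SAP are to be described in the study report.

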**Table 3: Estimated Margins for Kindolor Tosylate Based on HED Relative to the Starting Human Dose**

Species	Duration	Route	NOAEL Kindolor tosylate (mg/kg/day)	HED a Kindolor tosylate (mg/kg/day)	HED Kindolor tosylate (mg/day) b	Starting Dose in Humans Kindolor tosylate (mg)	FIH Starting Dose c Fold- lower relative to Rat HED
Rat	2 weeks	Oral	846	136	8160	100	82
Minipig	2 weeks	Oral	622	444	26,640	100	266

a The human equivalent dose (HED) was calculated by dividing the NOAEL by 6.2 for rats and 1.4 for micropigs and then multiplying by average body weight of 60 kg.

b Based on 60 kg human.

c Based on a proposed first-in-humans (FIH) starting dose of 100 mg and a proposed maximum dose of 1800 mg.

In the rat STZ model of PDN, 32.5 mg/kg and 40 mg/kg of kindolor (free base), equivalent to 45 mg/kg and 55 mg/kg kindolor tosylate, completely reversed tactile hyperalgesia. These doses produced plasma levels of 4.5-15.5  $\mu$ M kindolor. The HED at these efficacious doses in rats are 7.2 mg/kg and 8.8 mg/kg of kindolor tosylate, respectively, which for a 60 kg adult are doses of 431 mg and 530 mg kindolor tosylate, respectively.

In a CFA inflammatory pain model, 34.5 mg/kg kindolor tosylate (equivalent to 25 mg/kg kindolor free base) completely reversed thermal hyperalgesia in the rat. The HED of kindolor tosylate is 5.5 mg/kg for the 34.5 mg/kg effective doses in the CFA rat models. This method provides a preliminary estimate of a potentially effective dose of kindolor tosylate in human (331 mg for a 60 kg human).

Based on the above animal models, the highest dose in humans (1800 mg) is predicted to be approximately 3.6- to 6-fold higher than the predicted efficacious dose.

Thus, the dosing scheme, shown in [Table 5](#), brackets the potentially effective dose of 331 mg to 431 mg of kindolor tosylate for a 60 kg human while at the same time starting at a relatively low dose based on the toxicology profile in rats and minipigs.

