### **8.5. Day -1 Baseline and Final Eligibility Assessments Evaluated at Clinic Intake**

If the subject is eligible after performing all the initial screening assessments, s/he will be scheduled to start the study and will come to the clinic for a final eligibility check and complete the baseline assessments on Day -1. A sentinel cohort of 2 subjects (1 assigned to receive kindolor tosylate and 1 assigned to receive placebo) will be dosed and closely monitored for at least 24 hours after receiving drug for AEs, prior to clinic intake and dosing the remaining 6 subjects in each successive cohort. No more than 2 subjects will be dosed on a single day of these 6 subjects.

For final eligibility determination, the following will be assessed at clinic intake on Day -1:

- Medical/Surgical History update
- Physical Examination update
- Weight
- Vital Signs
- Birth control methods for men and women update
- Pregnancy test (women only) (must be obtained within 72 hours prior to dosing)
- Prior and Concomitant medications

For baseline, the following will be performed:

- Clinical laboratory tests including chemistry, amylase, lipase, hematology, coagulation, urinalysis, and urine drug/alcohol screen
- FOBT

Blood for DNA genomics will be collected if the subject is still eligible.

The screening period will not be extended. If the investigator determines that the subject could be a viable participant who could not for extenuating circumstances complete the screening period in 30-days, the subject can be re-screened by completing all of the screening assessments again. In this case, the subject will be assigned a new subject number.

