Routine monitoring visits by the clinical monitors and the sponsor will be scheduled at appropriate intervals but more frequently at the beginning of the study. A monitoring visit soon after the first two subjects have been treated is planned. At these visits, the monitors will verify that study procedures are being conducted according to the protocol guidelines, monitor eCRFs against source documents, review AEs and SAEs, and perform drug accountability. At the end of the study, they will confirm that the site has the appropriate essential documents on file, advise on storage of study records, and inspect the return and destruction records for unused investigational products.

**Sponsor Site Visits:** All investigators will allow the sponsor full access to study records during site visits by the sponsor. Visits by the sponsor will be made at a mutually convenient time and will be scheduled in advance.

**DSMB:** The UCSD DSMB will meet prior to the start of the study, and after each cohort completes the study. As each cohort completes the study, a Fast-Track unblinded statistician will generate the appropriate tables and listings including PK data and a Fast-Track physician will

compile this safety data and prepare a safety report for presentation to the DSMB in accordance with the Operating Charter and planned analyses. *Ad hoc* meetings will be convened if SAEs occur that are considered at least possibly related to the investigational product or clinical, laboratory, or AE findings meet any of the stopping criteria (see section [8.12.2](#)).

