#### **11.1.5. Gastrointestinal Adverse Events**

Gastrointestinal (GI) AEs will be assessed as follows:

- Stool Consistency Questionnaire – subject completed questionnaire ([Appendix A](#))
- GI Signs and Symptoms Checklist ([Appendix B](#))
- FOBT
- Open ended questions about AEs that are indicative of gastritis
- Clinical laboratory tests (hematocrit, hemoglobin, blood urea nitrogen (BUN), creatinine, ALT, and AST)
- Endoscopy (if indicated)

A-subject completed Stool Consistency Questionnaire ([Appendix A](#)) that asks 4 questions about GI symptoms will be utilized to assess GI AEs. The responses to the questions are based on a 4-point scale with 0 being no symptom and 3 being a severe symptom. The development of a new symptom or worsening of an existing symptom will be reported as an AE.

In addition, if a subject reports of any of the signs and symptoms of gastritis or potential GI ulcer complications or has a laboratory test result indicative of blood loss as shown in the GI Signs and Symptoms Checklist ([Appendix B](#)), the study gastroenterologist sub-investigator will do a thorough evaluation of the event and perform an endoscopy if it is considered warranted. A signs and symptoms checklist will be reviewed each day starting with Day 1, and then on Days 2, 3, and 7. Presence or absence of each sign or symptom will be recorded and if appropriate, a severity assessment or clinical significance evaluation will be performed.

Clinically significant changes in hematocrit and hemoglobin are defined as decreases of at least 10 percentage points and 2 g/dL, respectively. Clinically significant changes in other clinical laboratory tests will be defined as blood urea nitrogen  $\geq 40$  mg/dL, creatinine  $\geq 1.8$  mg/dL, ALT

and AST  $\geq 3$  times the upper limit of normal. If there is evidence of gastric erosion, ulcer, or bleeding in any subject confirmed by endoscopy or FOBT, the study will be stopped.

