### **11.2. Collection and Processing of Blood for PK Determinations**

Blood samples for determination of kindolor plasma concentrations will be collected by venipuncture within 15 minutes prior to dosing and at 0.25, 0.5, 1, 1.5, 2, 4, 8, 12, 24, and 48 hours after dosing. Blood will be collected as close to nominal times as possible and the date and time that each blood sample is collected will be recorded to the minute.

All plasma samples for each cohort will be analyzed for AUC(Tlast) and Cmax before enrolling the next cohort. If AUC(Tlast) exceeds 87,550 ng.h/mL or Cmax exceeds 13,490 ng/mL, then dose escalation will stop.

Further details on sample collection, processing, storage, and shipping are provided in the Manual of Procedures. Plasma concentrations will be determined using a validated liquid chromatography/mass spectrometry method.

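### The MTD rule names a dose even when no higher dose was shown to be intolerable, and it has no 'not reached' outcome

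*Protocol*

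**What the plan says.** The SAP (section 3.1) repeats the protocol's aim: "The primary objective of the study is to determine the safety and maximum tolerated dose (MTD) of kindolor tosylate in healthy volunteers".

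Protocol section 8.13.2 stops dosing within a cohort, or escalation to the next one, on any of four grounds: (a) the top dose has been reached; (b) a clinical, laboratory or AE criterion is met; (c) an exposure cap is exceeded; (d) the DSMB recommends stopping. Under (b), criteria i and ii and the laboratory part of iii are limited to subjects on active drug. The FOBT criterion is not: "Any subject has a positive FOBT". Section 11.1.5 has the same scope: "If there is evidence of gastric erosion, ulcer, or bleeding in any subject confirmed by endoscopy or FOBT, the study will be stopped".

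The section closes with the MTD definition: "The maximum tolerated dose (MTD) will be considered the highest dose where no active medication subjects meet the study stopping criteria". That sentence counts active subjects only.

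Dosing is staggered. A sentinel pair (1 active, 1 placebo) is observed for at least 24 hours before the other six are admitted, and then "No more than 2 subjects will be dosed on a single day of these 6 subjects" (section 8.5).

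The SAP reports FOBT results by treatment group (table shells 16 and 20) and whether a GI event triggered a stop (section 9.6). It contains no MTD derivation, and no MTD table appears in its list of tables.

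**The concern.** An MTD is normally understood as a limit: the dose below one that proved intolerable. The rule here returns a dose whether escalation ended because a limit was found, because the planned range ran out, or because a placebo subject had a positive stool test. The same label would cover three different results, and the label is a stated primary conclusion.

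The favourable outcome is affected as much as the unlucky one. If every cohort is clean, the trial reports an MTD of 1800 mg without having found a limit. If a placebo subject's FOBT ends the trial early, it reports a low MTD although no active subject met any criterion.

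**Working it through.** **The plan's own figures.** Protocol section 12.4 gives the chance of at least one event among 6 active subjects, 1 − (1 − p)^6. At p = 10%, 15%, 20% and 25% this is 46.9%, 62.3%, 73.8% and 82.2%, which reproduces the stated 47%, 62%, 74% and 82%.

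**Case A: four clean cohorts.**
1. Escalation stops under (a).
2. No active subject met a criterion at any dose.
3. The highest such dose is 1800 mg, so the rule returns 1800 mg as the MTD.

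What 0/6 at that dose shows about an event for which one case is enough to fail the dose:
- One-sided 95% upper limit: 1 − 0.05^(1/6) = 39.3%.
- Two-sided 95% upper limit: 1 − 0.025^(1/6) = 45.9%.
- Chance that the cohort is clean at a true rate of 10%: 0.9^6 = 53.1%. At 20%: 0.8^6 = 26.2%.

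**Case B: positive FOBT in a placebo subject only, cohort k = 1, 2 or 3.**
1. The FOBT criterion and section 11.1.5 apply to any subject, so the trial stops.
2. No active subject has met a criterion in this cohort or an earlier one.
3. The rule returns the current dose: 100, 300 or 900 mg.

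Number of active subjects behind that label: six if the cohort was fully dosed, fewer if dosing stopped within it. On the fastest schedule the other six are admitted on the sentinels' Day 2, and the first pair of them is dosed on the sentinels' Day 3. The sentinels' first scheduled post-dose FOBT is due that same day. If a sentinel placebo positive is known then, at most four subjects have been dosed, of whom two or three are active (the sentinel plus one or two from the pair, given the 5:1 allocation).

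**How likely is case B? Illustration only.** The documents give no false-positive rate. Let f be an assumed chance that a subject has at least one positive post-dose test unrelated to drug, and q = 1 − f. With 6 active and 2 placebo subjects per cohort, full dosing and testing, and no other kind of stop:

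P(placebo-only stop in cohorts 1 to 3) = Σ over k = 0, 1, 2 of q^(8k) × q^6 × (1 − q^2)

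| Assumed f | Cohort 1 | Cohort 2 | Cohort 3 | Total |
|---|---|---|---|---|
| 1% | 0.0187 | 0.0173 | 0.0160 | 5.2% |
| 2% | 0.0351 | 0.0298 | 0.0254 | 9.0% |
| 5% | 0.0717 | 0.0475 | 0.0315 | 15.1% |

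Competing stops would lower these totals. The logic of cases A and B does not depend on them.

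**The case against.** The strongest defence is that this is an operational definition, set in advance, in a descriptive study with no formal hypotheses (SAP section 6) and a capped dose range. Ground (a) is listed separately, so a reader can tell a capped result from a toxicity-limited one. The DSMB sees tables from an unblinded statistician, and the arm behind a positive FOBT will be visible in the SAP tables. The any-subject FOBT stop is sensible caution, and a label set too low errs on the safe side.

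Much of that stands. No subject is put at risk, no data are lost, and the FOBT stop should stay. It does not rescue the label, though: no text lets the DSMB or the SAP change what the rule returns, and the rule is the only provision for half of the primary objective.

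Three stronger readings are tempting and should not be adopted.

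- **A reader might infer that every exposure-cap stop also leaves the current dose as the MTD.** Section 11.2 says "If AUC(Tlast) exceeds 87,550 ng.h/mL or Cmax exceeds 13,490 ng/mL, then dose escalation will stop", which is about escalation. Section 10 uses the term for "clinical, laboratory, or AE findings meet any of the stopping criteria", which points to ground (b) alone. The MTD sentence, however, refers to study stopping criteria, matching the heading of section 8.13.2, and that heading covers (a) to (d). A Cmax above the cap in a single subject is best read as an active subject meeting a criterion, which disqualifies the dose. Only a stop on mean AUC, or on DSMB advice under (d), is ambiguous.
- **A reader might take the FOBT percentages as the expected risk.** They rest on assumed rates. The protocol also limits unrelated positives through its GI exclusions, dietary restrictions and pre-dose FOBTs.
- **A reader might infer that an early stop would wrongly place the limit below the effective dose**, because the dosing scheme "brackets the potentially effective dose of 331 mg to 431 mg of kindolor tosylate for a 60 kg human". The 331 mg figure is described as preliminary and is scaled from rats, so little rests on it.

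**Conclusion.** The rule is wrong as written. It names an MTD when no higher dose was shown to be intolerable: 1800 mg after four clean cohorts, and 100, 300 or 900 mg after a placebo-only positive FOBT in cohorts 1 to 3. Both results follow from the wording alone; the second assumes that no active subject had met a criterion by then.

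After four clean cohorts, 6 event-free active subjects at 1800 mg leave a true rate of up to 39% or 46% open. This is a small-sample limit that rewording cannot tighten, but it shows how little the label would rest on. An early stop could leave fewer than 6. The size of the FOBT risk cannot be determined from the documents. The fault lies in the stated primary conclusion, not in the conduct of the trial or the protection of subjects.

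**What to change.** Keep every safety stop, including the any-subject FOBT stop. In protocol section 8.13.2 and the SAP:

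1. Declare an MTD only if a higher tested dose met a stopping criterion in active subjects.
2. Otherwise report: MTD not reached / not determined; highest dose tested and tolerated X mg (n active dosed). Give the reason for stopping: top dose, placebo FOBT, exposure cap or DSMB.
3. State whether grounds (c) and (d) count as criteria for the MTD.
4. Add one SAP table by dose: active subjects dosed, and active subjects meeting each criterion.

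The cost is wording in two documents and one table. Dosing, sample size and safety stops do not change. The downside is that the trial may have to report that no MTD was found.
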